#### 5.4 **Supportive Care Guidelines**

Patients should receive full supportive care, including transfusions of blood and blood products, antibiotics, antiemetics, antidiarrheals, analgesics, etc., when appropriate. Bisphosphonates or denosumab are allowed for patients with bone metastases.

### 6. TREATMENT DISCONTINUATION

#### 6.1 **Removal of Subjects From Study**

Subjects who discontinue participation in the clinical study on their own or subjects who are withdrawn by the investigator, for reasons other than completion of treatment, disease progression or toxicity, will be defined as premature withdrawals.

Subjects who are not initiated on study drug, but sign informed consent and undergo at least some of the screening procedures will be considered screening failures. A record of these patients will be maintained by the study site.

#### 6.2 **Criteria For Study Treatment Discontinuation**

A subject will be discontinued from protocol therapy under the following circumstances:

- Any adverse event which, in the Investigator's opinion, requires termination of the study medication.
- Disease progression, unless at the discretion of the principal investigator (in collaboration with any co-sponsors or collaborators) continued treatment with study drug is appropriate.
- Substantial non-compliance (>25% of missed doses accounting for delays and dose modifications per protocol or instructions from research team staff for AEs), with the requirements of the study.
- The patient presents with a beta-HCG test consistent with pregnancy. Pregnancy will be reported along the same timelines as a serious adverse event.
- The patient uses illicit drugs or other substances that may, in the opinion of the Investigator, have a reasonable chance of contributing to toxicity or otherwise interfering with results.
- The development of a second malignancy that requires treatment, which would interfere with this study.

- The patient is lost to follow-up.
- Interruption in study drug administration for greater than 21 days (see Dose Modification section).
- Development of an intercurrent illness or situation which would, in the judgment of the investigator, affect assessments of clinical status and study endpoints to a significant degree.

The Investigator will make every reasonable effort to keep each patient in the study unless it is in the patient's best interests to discontinue participation. If a patient is removed from the study or declines further participation, all End of Treatment evaluations should be performed if the patient is willing and able to be assessed. A description of the reason(s) for withdrawal from the study must be recorded on the case report form (CRF). The Investigator should also ensure that all patients are followed up for survival status after the Final Visit.

Relevant visit data should be entered on the CRF and any unused study medication will be accounted for and returned for all patients participating in the study, even for a brief period of time. Patients who discontinue following entry will have relevant information completed and recorded on the CRF. All patients who discontinue because of adverse events or clinically significant laboratory abnormalities should be followed up until they recover or stabilize, and the subsequent outcome will be recorded. If any patient should die during the trial or within 30 days of stopping study treatment, the Investigator will inform the UF Health Data Integrity and Safety Committee.

### 6.3 **Replacement of Subjects**

Subjects will be replaced if they have not received any doses of study drug prior to their continuing participation in the protocol for any reason, or if the patient wishes to discontinue participation in the protocol, but is not discontinued for disease progression, toxicity, or any of the reasons listed in section 6.2.

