### 5.1 **Treatment Schedule/Administration**

All participants will have unresectable, previously-treated squamous cell NSCLC who have previously been treated with a platinum doublet (or have refused such prior therapy); those who have a molecularly targetable genetic mutation in their tumor must have also received the appropriate specific therapy for that mutation.

Both men and women of all races and ethnic groups will be eligible for this trial. This study was designed to include women and minorities, but will not be designed to measure differences of intervention effects. Men and women will be recruited with no preference to gender. No exclusion to this study will be based on race. Minorities will be actively recruited to participate.

Eligible subjects will include those with radiographically-staged locally advanced or metastatic NSCLC who have received any prior therapy for the lesion(s). Patients who receive radiation therapy to any indicator lesion must have demonstrated progressive growth of the lesion to be assessable; be willing to use contraception; are neither pregnant nor lactating; are greater than 18 years old and have an anticipated life expectancy of at least 12 weeks; have normal end-organ function and limited comorbidities, and are able to provide written informed consent.

Upon confirmation of eligibility and provision of written informed consent, subjects will receive TAS-102 (Lonsurf®) at its FDA-approved dose and schedule, 35 mg/m^2 up to a maximum of 80 mg per dose (based on the trifluridine component) orally twice daily within one hour of completion

of morning and evening meals on Days 1 through 5 and Days 8 through 12 of each 28-day cycle until disease progression or unacceptable toxicity. Doses will be rounded to the nearest 5 mg increment. Additional doses will not be taken to make up for missed or held doses. Subjects will be monitored weekly during the first cycle for tolerance, and tumor status will be assessed every other cycle. Participants will continue on therapy until the development of unacceptable toxicity, disease progression, or participant desire to discontinue protocol therapy. There is no set maximum of cycles, as patients who have responded and who are tolerating this regimen may continue it until withdrawal of consent, disease progression, development of undue toxicity, or death.

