### **11. STATISTICAL METHODS**

#### **11.1 Sample Size Determination**

This is a pilot phase II study, so we are interested in evaluating the feasibility and safety of a regimen of daily TAS-102 administered to subjects with squamous cell lung cancer. To minimize the number of subjects exposed, the sample size will be determined by the anticipated response rate. A response rate of 20% or above to TAS-102 will be of interest in subjects with previously-treated squamous cell lung cancer. Initially, 14 subjects will be evaluated for response, and if none of the 14 evaluable subjects experiences a partial or complete response, then the study will be terminated. If the true response rate is 20%, the chance of rejection error is less than 5%. However, in the event of one response among the first 14 subjects, further accrual will continue to a total of 30 evaluable subjects to estimate the response rate more precisely with a standard error of no more than 9%. A subject is considered eligible for toxicity evaluation if they have received at least one dose of TAS-102. A subject will be considered eligible for evaluation of activity if they have also received two cycles of therapy as planned.

Based upon the numbers of subjects seen at the University of Florida Cancer Center clinics and our accrual to other similar studies, it is estimated that accrual to the first level (14 subjects) will be completed within nine months. If the study is fully accrued (30 subjects) and at least the last such subject derives benefit from the anticipated maximal number of six cycles, then the length of the entire study will be approximately 24 months.

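### Section 6.3 replaces treated patients who stop by choice without saying whether they stay in the response denominator, which probably biases the response rate modestly upward

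*Combined protocol and SAP*

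**What the plan says.** Section 6.3 gives two alternative grounds for replacement. The first is that no drug was taken: "Subjects will be replaced if they have not received any doses of study drug". The second is the patient's own choice: "or if the patient wishes to discontinue participation in the protocol, but is not discontinued for disease progression, toxicity"; stops for a section 6.2 reason are likewise outside this ground. The second ground does not require that the patient be undosed or unscanned, and it sets no time limit.

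The second ground is not empty. The patient's own wish is not among the 6.2 reasons, which include progression, adverse events, substantial non-compliance, long interruption and loss to follow-up ("The patient is lost to follow-up"). Section 5.1 lists it as a reason of its own for ending therapy: "unacceptable toxicity, disease progression, or participant desire to discontinue protocol therapy". Section 6.1 also recognises the group: "Subjects who discontinue participation in the clinical study on their own".

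The efficacy counts are fixed numbers of evaluable subjects. For stage 1, section 11.1 says "Initially, 14 subjects will be evaluated for response, and if none of the 14 evaluable subjects experiences a partial or complete response", the study stops. Otherwise "further accrual will continue to a total of 30 evaluable subjects". Section 11.1 makes a subject evaluable for activity after two cycles as planned. Section 8.1 asks for measurable disease, one cycle and a re-evaluation. Section 11.2 estimates the response rate with an exact 95% interval but names no all-treated set for it, whereas section 11.4 includes everyone who received study drug in the safety analysis.

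**The concern.** Leaving by choice is unlikely to be independent of outcome. A patient with stable disease who feels no benefit has more reason to go than a patient whose tumour is shrinking, and may go before RECIST progression is recorded. If that patient's place passes to a new subject, a known non-response is exchanged for a fresh chance of response.

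This would affect two results: the primary response rate, and the 0-of-14 rule, which is the only futility check in the plan. The margin is narrow: section 1.1 puts response to untargeted salvage agents below 10%, and section 11.1 sets 20% as the rate of interest.

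**Working it through.** **The plan's own figures.** With a true rate of 20%, the chance of 0 responses in 14 is 0.8^14 = 0.0440, which agrees with the stated error below 5%. The standard error at n = 30 is √(0.20 × 0.80/30) = 7.3%, and at most √(0.25/30) = 9.1%, which agrees with the stated 9% to rounding.

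**Who is affected.** The first scheduled on-study scan comes just before Cycle 3, at about week 8 (2 × 28 days).

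- Leaves by choice before two cycles: already outside the 11.1 activity set. Because 14 and 30 evaluable subjects are needed, 11.1 alone would bring in another patient.
- Leaves by choice after two cycles and a scan without response: evaluable under both 8.1 and 11.1 (given measurable disease). Only 6.3 can take this patient's place away.
- Stopped for progression, toxicity or a 6.2 reason: not replaced under 6.3.

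What 6.3 adds is therefore mainly the second group.

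**Size.** Let p be the true response rate and w the share of non-responders who are replaced. The documents give no value for w; 5%, 10% and 20% are assumptions. Responders are assumed to stay. The chance that a treated patient keeps the place is p + (1−p)(1−w) = 1 − (1−p)w, so the expected rate among those kept is p/[1 − (1−p)w].

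| w | True 10% becomes | Chance of 0/14 at true 10% | True 20% becomes |
|---|---|---|---|
| 0 | 10.0% | 0.9^14 = 22.9% | 20.0% |
| 5% | 0.10/0.955 = 10.5% | 21.3% | 0.20/0.96 = 20.8% |
| 10% | 0.10/0.91 = 11.0% | 19.6% | 0.20/0.92 = 21.7% |
| 20% | 0.10/0.82 = 12.2% | 16.2% | 0.20/0.84 = 23.8% |

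The third column is (1 − expected rate)^14.

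**Which w is plausible.** Section 1.1 gives response below 10% and clinical benefit of about 50%. Taking response as 10%, stable disease is about 50 − 10 = 40% of patients. If the patients whom 6.3 adds all come from that group, w = 5% is 0.05 × 90 = 4.5% of patients, or 4.5/40 = 11% of stable patients leaving purely by choice. For w = 10% it is 9/40 = 22.5%, and for w = 20% it is 18/40 = 45%. The lower end is more credible.

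**Dependence on direction.** Now let v be the share of all treated patients replaced, and k the ratio of their response rate to the overall rate. The expected rate is p(1 − vk)/(1 − v). At p = 10% and v = 10%, this is 11.1% for k = 0, 10.6% for k = 0.5 and 10.0% for k = 1. If 5% of treated patients left and all were responders, the rate would fall to (0.10 − 0.05)/0.95 = 5.3%.

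**Example.** Six responses in 30 kept patients is 20.0% (exact 95% CI 7.7% to 38.6%). Counting three replaced treated non-responders gives 6/33 = 18.2% (7.0% to 35.5%), below the rate of interest.

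**The case against.** The strongest reply is that 6.3 says a subject is replaced and no more. It does not say that the subject's data leave the analysis. Under 8.1 an evaluable patient has the response classified, and nothing in 6.3 overrides that, so replacement might only add a patient. This stands as to the wording: a reader might infer that 6.3 expressly removes non-responders from the first 14 and the final 30, and the documents do not say so. But the counts are fixed and no all-treated response set is named. On that footing the natural meaning of replacement is that the newcomer takes the place, and nothing in the plan says otherwise.

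Second, for patients who leave before two cycles, 11.1 already causes the same bias without 6.3. This also stands. The effect of 6.3 comes on top of it, and correcting 11.1 alone would leave the later route open.

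Third, the direction is assumed. No source in the documents says that responders rarely leave, and a responder who left by choice would also be replaced, which lowers the rate. Upward bias is the likelier result, but not a certain one.

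Fourth, there are partial safeguards. Section 6.2 asks for end-of-treatment evaluations if the patient is willing, section 8.2 asks for efforts to document progression after symptomatic deterioration, and section 3.1 caps enrolment at 30. They help little. The off-therapy measurements in 7.4 include no imaging. The cap does not restrain replacement among the first 14, and at the final stage it conflicts with a target of 30 evaluable subjects.

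**Conclusion.** The point holds as a gap in the rules with a probable, modest upward bias. Section 6.3 lets a treated patient who leaves by choice be replaced at any time, and the plan does not say whether that patient still counts. If the place is lost and only non-responders leave, a true 10% is reported on average as about 10.5% to 12.2%, and the chance of stopping at 0 of 14 falls from 22.9% to between 21.3% and 16.2%, for w from 5% to 20%. Because progression, toxicity and all 6.2 reasons are excluded from replacement, the lower end is more plausible. A shift of 0.5 to 2.2 points is below the standard error of √(0.10 × 0.90/30) = 5.5 points at n = 30, but a larger sample would not remove it.

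A reader might conclude that the plan certainly inflates the rate, by a known amount. The documents do not support that: they give no withdrawal rate, the direction is an inference, and the loss of the place is a reading of 6.3, not its text. It should be corrected because the remedy is simple and needs no added patients.

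**What to change.** In 6.3, limit replacement to subjects who took no TAS-102 and delete the second ground. In 6.3, 8.1 and 11.1 together (and in the synopsis, which repeats the 11.1 text), state that every treated subject keeps his or her place in the first 14 and in the final denominator, and counts as a non-responder unless a confirmed CR or PR was recorded. Changing 6.3 alone would contradict the one-cycle and two-cycle evaluability definitions and leave the earlier exclusions in force. Report the rate in the evaluable set as a sensitivity analysis.

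The cost is a few sentences in several sections. No patients or procedures are added. The downside is that the reported response rate may be slightly lower. The change also eases the conflict between the cap of 30 enrolled in 3.1 and the 30 evaluable in 11.1.

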### 6.4 **Study Discontinuation**

It is unlikely that the trial itself will require a premature termination. However the trial will be stopped prematurely (prior to completion of accrual, protocol therapy, and follow-up) for safety reasons if the therapy at Dose level 0 is intolerable in the first six patients, requiring dose reduction to Dose level -1.

## **7. STUDY PROCEDURES**

### 7.1 **Study Schedule of Events**

Day of Protocol	Baseline 	Day 1 Each Cycle	Day 15 Each Cycle	Day 1, odd cycles (beginning with Cycle 3)	Off Treatment	Follow Up
Studies:						
H&P / PS / VS & TOX	X	X			X	X
CBC w/ Diff.	X	X	X		X	X
CMP	X	X			X	X
UA and Pregnancy Test	X					
Diagnostic Imaging Scan / TA	X			X		X
ECG	X					
Concomitant Medications	X	X	X		X	X
Adverse Events	X	X	X		X	X
Treatment:						
TAS-102(Lonsurf®)		X				

1) Abbreviations: H&P=History and Physical examination; PS=ECOG performance status; VS=vital signs (blood pressure, temperature, pulse and respiratory rates, weight and height); TOX=toxicity assessment; CBC/diff=complete blood count and white blood cell differential; CMP=12 item complete metabolic profile (sodium, potassium, chloride, bicarbonate, blood urea nitrogen, creatinine, glucose, alkaline phosphatase, AST, ALT, total bilirubin, uric acid); UA=urinalysis; Pregnancy test only for women of childbearing potential. For the first cycle, the H&P, toxicity assessment, CBC and CMP are repeated weekly (Days 1, 8, 15 and 22).

2) Baseline studies are repeated on day 1 if there are more than 14 days between baseline and day 1. The radiographic assessment must be repeated if there are more than 21 days between baseline and day 1.

3) TA= Tumor assessment by RECIST Criteria by diagnostic CT scan, PET/CT scan and/or MRI scan. Scans are to be done within one calendar week prior to Day 1 of every odd-numbered cycle (beginning with Cycle 3).

4) TAS-102 (Lonsurf®) is initially dosed as 35 mg/m^2 up to a maximum of 80 mg per dose (based on the trifluridine component) orally twice daily within one hour of completion of morning and evening meals on Days 1 through 5 and Days 8 through 12 of each 28-day cycle. Doses will be rounded to the nearest 5 mg increment.

Follow up evaluations are also performed as appropriate clinically

## 7.2 Screening Evaluations

Written informed consent must be obtained prior to performing any study-specific evaluations or tests. Tests or evaluations performed as standard of care within the specified screening period, but prior to informed consent, may be accepted for this study and need not be repeated.

Height, weight and performance status

Physical exam

Concomitant medication collection

Laboratory studies:

- CBC with differential count

- Comprehensive metabolic panel, serum magnesium
- ECG
- Urine pregnancy test (females of potential child-bearing status only)
- CT or MRI of thorax and abdomen, or PET/CT

### 7.3 On-Study Evaluations

#### **Each week of first cycle (days 1, 8, 15 and 22):**

Weight and performance status

Physical exam

Concomitant medication collection

Adverse event collection

Laboratory studies

- CBC with differential count
- Comprehensive metabolic panel, serum magnesium

#### **First day of each cycle (within 3 days):**

Weight and performance status

Physical exam

Concomitant medication collection

Adverse event collection

Laboratory studies

- CBC with differential count
- Comprehensive metabolic panel, serum magnesium

#### **Day 15 of each cycle:**

Concomitant medication collection

Adverse event collection

Laboratory studies

- CBC with differential count

#### **First day of every odd-numbered cycle (beginning with Cycle 3):**

- CT or MRI of thorax and abdomen, or PET/CT (must be obtained within one calendar week prior to first day of each odd numbered cycle)

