### 5.3 Dose Modifications

The National Cancer Institute (NCI) Common Toxicity Criteria for Adverse Events Version 4 (CTCAE) will be used to grade toxicity (<http://evs.nci.nih.gov/ftp1/CTCAE/About.html>).

The starting dose of TAS-102 is 35 mg/m^2 up to a maximum of 80 mg per dose (based on the trifluridine component) orally twice daily within one hour of completion of morning and evening meals on Days 1 through 5 and Days 8 through 12 of each 28-day cycle until disease progression or unacceptable toxicity. Doses will be rounded to the nearest 5 mg increment. Study medication will be administered on a 4 week schedule. Doses will be delayed or reduced for clinically significant (Grade 3-4) hematologic and non-hematologic toxicities that are related to protocol therapy according to the guidelines shown in the Dose Delays/Dose Modifications table that follows. Dose modifications will follow predefined dose levels. Dose adjustments for hematologic toxicity are based on the blood counts obtained in preparation for the day of treatment.

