#### 5.3.1 Dose Modification Table

Dose level 0 (standard starting dose)	35 mg/m  po bid
Dose level – 1	30 mg/m  po bid
Dose level – 2	25 mg/m  po bid

Inpatient dose reduction and dose interruption will be permitted once a patient has experienced drug-related toxicity provided that the criteria for patient withdrawal from study treatment have not been met. All inpatient dose reductions are relative to the lowest dose of the current cycle.

For all toxicities, doses of TAS-102 will be modified based upon Day 1 and Day 15, complete blood cell counts. Day 1 TAS-102 dosing for each cycle will be held until:

- Absolute neutrophil count (ANC) is greater than or equal to 1,500/mm^3 or febrile neutropenia is resolved

- Platelets are greater than or equal to 75,000/mm^3
- Grade 3 or 4 non-hematological adverse reactions are resolved to Grade 0 or 1

Within a treatment cycle, TAS-102 will be withheld for any of the following:

- Absolute neutrophil count (ANC) less than 500/mm^3 or febrile neutropenia
- Platelets less than 50,000/mm^3
- Grade 3 or 4 non-hematological adverse reactions

After recovery, resume TAS-102 after reducing the dose by 5 mg/m^2/dose (as above) from the previous dose level, if the following occur:

- Febrile neutropenia
- Uncomplicated Grade 4 neutropenia (which has recovered to greater than or equal to 1,500/mm^3, or baseline in subjects with benign ethnic neutropenia) or thrombocytopenia (which has recovered to greater than or equal to 75,000/mm^3) that results in more than 1-week delay in start of next cycle
- Non-hematologic Grade 3 or Grade 4 adverse reaction except for Grade 3 nausea and/or vomiting controlled by antiemetic therapy or Grade 3 diarrhea responsive to antidiarrheal medication

If a subject experiences more than one toxicity, dose reduction should be according to the toxicity with the highest grade. In the case of two or more toxicities of the same grade, the investigator may dose reduce according to that deemed most causally related to study treatment. If more than 3 dose reductions are required, TAS-102 will be discontinued. Do not escalate dose after it has been reduced.

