### **5.3.2 Non- Hematologic Toxicity**

For Grade 3 and 4 toxicities, treatment should be withheld until the toxicity resolves to Grade 1 or less (or to baseline), then reinstated (if medically appropriate) at a one level dose reduction. Nausea and vomiting or diarrhea must persist at Grade 3 or 4 despite maximal medical therapy. All agents should be dose reduced in cases where either agent may be the cause of a given toxicity. Patients must meet pre-treatment laboratory criteria (as specified in the inclusion criteria) at Day 1 of each cycle to receive therapy administration. Patients will not be eligible for further treatment if resolution of toxicities requires a greater than 3-week delay in the start of the next cycle (five weeks from the start of the prior cycle).

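### Tumour scans are tied to cycle number with no calendar anchor, so delayed cycle starts postpone them and tend to lengthen mean measured PFS

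*Combined protocol and SAP*

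**What the plan says.** Every statement on the timing of on-treatment imaging counts in cycles. Section 7.3 says that the scan "must be obtained within one calendar week prior to first day of each odd numbered cycle". Footnote 3 of the section 7.1 schedule says "Scans are to be done within one calendar week prior to Day 1 of every odd-numbered cycle (beginning with Cycle 3". Section 5.1 says that "tumor status will be assessed every other cycle", and the synopsis uses the same odd-cycle anchor. Cycles are nominally four weeks long, with dosing on "Days 1 through 5 and Days 8 through 12 of each 28-day cycle" (section 5.3).

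Cycle starts can move. Under section 5.3.1, "Day 1 TAS-102 dosing for each cycle will be held until" neutrophil, platelet and non-hematologic criteria are met. The limits on how long a start may slip differ:

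- Section 5.3.3 (hematologic) ends treatment after a delay of more than 2 weeks.
- Section 5.3.2 (non-hematologic) ends it when recovery needs a "greater than 3-week delay in the start of the next cycle (five weeks from the start of the prior cycle".
- Section 6.2 ends it after an interruption of more than 21 days.

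PFS is a secondary endpoint. Section 11.2 plans Kaplan-Meier mean estimates and curves, and gives no rule for late or missed assessments.

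**The concern.** Progression on imaging can be dated only when someone looks. If the scan waits for the next odd cycle and that cycle waits for recovery, the assessment interval lengthens with toxicity. Patients with the most holds are then scanned least often, and their progression is on average recorded later for a reason unrelated to disease control. In a single-arm trial PFS is informative mainly beside outside data, which needs a stable and comparable assessment interval. Holds are foreseeable: section 9.1.7 quotes Grade 3-4 neutropenia at 38%. The documents give no rate of cycle delay.

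**Working it through.** **The plan's own figure.** The documents give no PFS assumption, event count or power. The only error figure is in section 11.1: a chance below 5% of stopping on 0 responses in 14 if the true response rate is 20%. That is 0.8^14 = 0.044, so it reproduces. Scan timing does not enter the calculation.

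**Scan dates.** If each cycle starts d days late, scan k falls at Day 1 + 2k(28 + d).

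| Delay per cycle | First scan | Slip | Interval |
|---|---|---|---|
| 0 days | Day 57 | none | 8 weeks |
| 7 days | Day 71 | 14 days | 10 weeks |
| 14 days | Day 85 | 28 days | 12 weeks |
| 21 days | Day 99 | 42 days | 14 weeks |

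The 14-day row is the limit in section 5.3.3 and the 21-day row is the 3-week limit in section 5.3.2. The parenthesis in section 5.3.2 does not fit its own sentence. A 3-week delay puts the next start at 28 + 21 = 49 days, or 7 weeks, after the prior one. Five weeks is 35 days, a delay of 7 days.

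**Effect on mean PFS.** I simulated 200,000 patients per scenario with exponential progression times. Measured PFS is the first scan on or after true progression. Cycle-anchored scans are compared with fixed scans every 8 weeks. The true medians and the delay rates are assumptions. The table gives the rise in mean measured PFS, in months.

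| True median | 20% of cycles, 7 d | 20%, 14 d | 38%, 7 d | 38%, 14 d | 60%, 7 d | 60%, 14 d |
|---|---|---|---|---|---|---|
| 2 months | 0.06 | 0.13 | 0.11 | 0.24 | 0.17 | 0.36 |
| 3 months | 0.06 | 0.12 | 0.11 | 0.22 | 0.17 | 0.34 |
| 4 months | 0.06 | 0.12 | 0.10 | 0.22 | 0.16 | 0.33 |

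The shift is upward in every cell, from about 0.05 to 0.4 month. The 38% columns borrow the neutropenia figure only as a stand-in for a delay rate.

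**Effect on the median.** Scan dates are discrete, so the median moves in steps. With 38% of cycles delayed by 14 days it goes from 3.68 to 4.14 months at a true median of 3, but from 5.52 down to 5.06 at a true median of 4.

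**Effect by patient.** After a single 14-day delay before Cycle 2, and across true medians of 2 to 6 months, 78-83% of simulated patients have longer measured PFS and 17-22% have shorter. The shorter group progressed just after the planned scan date, so the late scan caught them before the next planned one would have.

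**Effect on stable disease.** With a true median of 3 months (assumed), the proportion still progression-free at time t is 2^(-t/median). This gives 65% at week 8, 59% at week 10, 53% at week 12 and 48% at week 14. A later first scan therefore finds fewer patients with documentable stable disease, which lowers the clinical benefit rate.

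**Duration of response.** Section 8.2 dates its start and its end by scans. Both can move, so the net direction is undetermined.

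**The case against.** The strongest reply is that this is immaterial. PFS is secondary and descriptive, with no hypothesis. Section 11.2 plans no PFS comparison, and the historical comparison in section 11.3 concerns demographic and baseline characteristics. With 30 events and a 3-month median, an approximate 95% interval is 3 × exp(±1.96/√30), or 2.1 to 4.3 months, far wider than the shift. The 8-week interval itself adds about 1 month (true mean 4.34 against 5.32 months measured at a 3-month median), and re-anchoring leaves that in place. The simulation also omits deaths, palliative radiotherapy counted as progression (section 5.2) and clinically indicated evaluations (sections 7.1 and 7.5), all of which would shrink the difference. A scan just before Day 1 also informs the decision to continue. All of this stands, and it keeps the point minor.

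A reader might infer that every toxicity hold postpones a scan. The documents do not support that. Section 5.1 says "Additional doses will not be taken to make up for missed or held doses", so a hold within a cycle need not move the next Day 1. A scan may also be done before a Day 1 hold is declared, because its window opens a week ahead while section 7.3 allows Day 1 laboratory work within 3 days. That is only partial protection: a delay before Cycle 2 moves the Cycle 3 scan anyway, and a scan done on time before a two-week hold falls outside the window as written.

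A reader might also pair the 38% neutropenia figure with a 6-week slip. Neutropenia falls under the 2-week limit. The 6-week figure needs two maximal non-hematologic delays, each of which carries a dose reduction under section 5.3.2. Section 5.3.3 removes patients who need two reductions, while section 5.3.1 stops treatment only when more than three are required. Those passages also need reconciling.

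**Conclusion.** The point holds as a minor one. Scheduled scans follow cycle number alone, delayed cycle starts push them back, and the analysis plan does nothing to offset it. Mean PFS, the summary that section 11.2 names, tends to come out longer by about 0.05-0.4 month. That range assumes 20-60% of cycles delayed by 7-14 days, a true median PFS of 2-4 months, exponential progression, and detection only at scheduled scans.

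It would be wrong to conclude that the schedule uniformly flatters the drug. The median can fall, the clinical benefit rate can fall, and duration of response has no determined direction. The first scan can slip by up to 4 weeks under section 5.3.3 or 6 weeks under the 3-week wording of section 5.3.2, but only 2 weeks if that section's parenthesis governs. The 14/30 design does not use scan timing and is unaffected.

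**What to change.** In the synopsis, 5.1, 7.1 and 7.3, schedule tumour assessments every 8 weeks from Cycle 1 Day 1, the plan's own nominal interval, with the existing one-week window and regardless of treatment delays. Separately, reconcile the delay limits in sections 5.3.2 (including its parenthesis), 5.3.3 and 6.2, since they determine how far a cycle start can move.

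The change is wording only and adds no patients. In delayed patients a scan may no longer coincide with a Day 1 visit, and an occasional extra scan may be needed over a long course. It does not remove the lag from the 8-week interval itself. It also does not cover patients who stop treatment before progression, for whom section 7.5 leaves imaging to clinical indication.
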